#### 2.2 Design

The study will be a randomized double-blind, placebo-controlled multi-center trial of Aggrenox compared to placebo for the prevention of access failure in patients who receive a new arteriovenous graft. Eligible subjects will be enrolled and baseline data collected prior to the placement of a new graft. Following successful placement of the graft, subjects will be randomized with equal allocation to therapy with either Aggrenox 1 capsule twice a day or a matched placebo. For randomization, subjects will be stratified by Clinical Center and whether the graft placement is in the lower arm or at another site (e.g., upper arm or leg) and whether or not the patient is using an ACE inhibitor or angiotensin receptor blocker at enrollment. The study medication will be started within 2 days of the access surgery and continued until the primary endpoint. The primary outcome will be primary unassisted patency, defined as the time from randomization until the composite endpoint of thrombosis or any access procedure required to maintain or restore access function (subsequently referred to as the first access event). Predefined secondary outcomes include 1) the time from randomization to site failure, 2) time from randomization to death, and 3) time from randomization to the composite outcome of site failure or death. The study participants will be followed monthly to measure access flow rate and record access related complications, adverse drug reactions, hospitalizations, and medication compliance until the primary endpoint is reached. Monthly measurement of access flow rate will be used to detect a hemodynamically significant stenosis before it leads to access thrombosis. A drop in monthly access flow rate that meets pre-specified limits will trigger angiographic evaluation and repair of the access if a 50% or greater stenosis is observed. The study drug and active monitoring will be discontinued when the primary endpoint is reached. Further follow-up will be limited to determining whether total access site failure or death occurred prior to

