#### 4. STUDY TREATMENT PLAN

#### 4.1 Study Visits

Subjects should be seen prior to creation of the access for enrollment and collection of baseline data. The subject will be evaluated again within 2 days after creation of the new access to confirm that an eligible graft had been placed and is patent. If the access is patent, the subject will be randomized into the study and the first months supply of study medication will be provided. The patient will be asked to take their first dose of medication at that time.

Following randomization, subjects will be seen at monthly intervals throughout the duration of the study. It is anticipated that most subjects will be undergoing hemodialysis and will be seen at the time of a scheduled hemodialysis session. For subjects on hemodialysis, each monthly visit will include a measurement of access flow rate along with collection of study data including an assessment of access related procedures, complications, hospitalizations and compliance with the study medication (Section 6.2 below). For those subjects not yet on hemodialysis a monthly visit will need to be arranged to assess access patency and collect study data.

The subject will remain on study medication until the primary endpoint is reached, at which point the medication will be terminated. The monthly visit schedule will continue until the first regularly scheduled monthly visit following the primary endpoint. At closeout, the functional status of all accesses and survival of all patients that had been enrolled in the study will be determined and if total site failure or death has occurred, the time of these events will be recorded. Each monthly visit will include an assessment of potential adverse events.

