#### 4.4 Events Leading to Withdrawal from the Study

A patient will be withdrawn from the study for the following reasons:

- 1. Death
- 2. Loss to follow-up due to permanent transfer to another renal replacement modality or to a nonparticipating dialysis unit.
- 3. Withdrawal of consent.

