#### 6.2.7 Study Closeout

At completion of the study it will be determined whether the access that was randomized into the study is still functional or not. If total site failure has occurred the date of that occurrence will be determined. Hospitalization and mortality data will be obtained using national databases while the study is on-going and for up to five years after the study has ended.

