#### 8. SECONDARY OUTCOME MEASURES

#### 8.1 Cumulative Patency: Time to Complete Access Site Failure

Complete loss of a functional access site is an outcome of major clinical importance. It is not economically feasible to continue the study drug and intensive monthly data collection for the duration needed for an adequately powered study of site failure. However, it is important to track this outcome at the closeout of the study to see if the trend is consistent with the effect seen for the study drug in the main trial. For this analysis, cumulative patency is the time from randomization to complete loss of the access site for dialysis regardless of the number of interventions required to restore or maintain patency. Loss of the access site is defined by the need to place a new access using new arteriotomy and venotomy incisions or by the abandonment of the prior access as defined by the need for a central venous dialysis catheter for a period of  $\geq 1$  month. Operationally the need for a new arteriotomy and venotomy sites will be detected by the need for a completely new site for the placement of the access. (Note that in most instances a chart review should not be needed to determine this endpoint). Procedures used to prolong the function of the access at the current site such as resection and replacement of part of the graft or changing just the site of the venous anastomosis will not be considered site failure). It is anticipated that a pharmacological agent that prolongs primary unassisted patency will also prolong cumulative patency even if the drug is stopped at the primary endpoint. The median cumulative patency in a control population without active flow monitoring and angioplasty is expected to be about 2 years [Hofstra, 1996 #60; Mattsson, 1997 #280; Kohler, 1999 #281]. An active access surveillance program will prolong access survival in the control population beyond 2 years but the exact duration is not well defined in the literature [Sands, 1995 #63; Safa, 1996 #101; Besarab, 1995 #62].

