#### 9.2.2.4 Secondary Outcomes

Time from randomization to the secondary outcome of site failure will be analyzed using a Cox regression model similar to that used in the primary analysis, with the same stratification factors, adjustment for baseline serum albumin and the same censoring variables. Time from randomization to death, and time from randomization to the composite of death or site failure will also be analyzed by Cox regressions with the same stratification factors and adjustment for baseline albumin as in the primary analysis. As for the primary analysis, censoring events include renal transplant, switch to peritoneal dialysis or home dialysis, or transfer to a center not participating in the trial. Cox models with cause-specific hazard rates will be used to analyze the specific cause of the primary events (e.g., events may be classified as being triggered by stenosis or clotting).

The effect of Aggrenox on the change in access blood flow over time (considered as a continuous variable) will be examined by longitudinal mixed effects models (100) or generalized estimating equations (101, 102). Joint models incorporating the longitudinal changes in access blood flow and the time-to-first access procedure will also be considered (103).

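### Time to death, and death or site failure, are censored at transplant, modality switch or transfer, although the protocol plans to learn of later deaths

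*Protocol*

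**What the plan says.** **The censoring rule.** Section 9.2.2.4 covers three time-to-event secondary outcomes. Site failure is modelled "with the same stratification factors, adjustment for baseline serum albumin and the same censoring variables" as the primary analysis. For time to death, and for death or site failure, "censoring events include renal transplant, switch to peritoneal dialysis or home dialysis, or transfer to a center not participating in the trial". The primary list in Section 9.2.2.2 also contains death and this one does not, so the list was written with the death outcomes in mind.

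**What will be known.** Section 4.1 states: "At closeout, the functional status of all accesses and survival of all patients that had been enrolled in the study will be determined". The dates of any site failure or death are recorded too. Section 2.2 describes the period after the primary endpoint in the same terms: "Further follow-up will be limited to determining whether total access site failure or death occurred prior to" closeout. Section 6.2.7, like Section 4.5, adds: "Hospitalization and mortality data will be obtained using national databases while the study is on-going", and for up to five years afterwards.

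**What points the other way.** Section 4.4 lists among the reasons for withdrawal: "Loss to follow-up due to permanent transfer to another renal replacement modality or to a nonparticipating dialysis unit". Section 11.2 lets patients withdraw consent to database access, and makes release of the Social Security number subject to extra written consent where the local IRB requires it.

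**The concern.** Section 9.2.2.2 gives two reasons for censoring the primary outcome: earlier access-survival studies did so, and adding these exits to the endpoint would dilute the hypothesised effect on patency. Neither reason carries over to mortality. A patient who is transplanted, changes modality or moves unit can still die, and counting that death adds no transplant or transfer to the endpoint.

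The exits may also be related to prognosis. Section 9.2.2.2 concedes that they are frequent and that censoring them risks bias, but Section 9.2.2.3 examines that risk for the primary Cox model only. The mortality model has the same exposure and no check.

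The outcome matters. Section 8.2 makes death a secondary outcome because the drug must not do harm that outweighs its benefit, and it concedes limited power. Section 1.5 raises a possible survival benefit. Both questions are better answered with every death that the trial can ascertain.

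**Working it through.** **No stated figure to reproduce.** The protocol gives no expected number of deaths and no power for mortality. Its sample size agrees with its own accrual inputs (0.31 × 1136 grafts per year × 3 years = 1056.5, against 1056), and N = 1056 is used below.

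**Inputs**
- Annual mortality 16% (Section 1.3). The sentence says survival, but it is set against 8% annual mortality in an earlier study, so it is read as mortality.
- Annual death, modality transfer or loss combined 22% (Sections 9.1 and 9.1.3).
- Follow-up per patient, with uniform accrual and no early stop: 1 to 4 years (3 years of accrual, 4 in total) or 0.5 to 4.5 years (48+6-month addendum, Section 9.1).
- Assumption: constant hazards, with the non-death exit hazard obtained by subtraction, because the protocol does not split the 22%.

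**Hazards per year**
- Death: λ = −ln(0.84) = 0.174
- Death or exit: Λ = −ln(0.78) = 0.248
- Non-death exit: c = 0.248 − 0.174 = 0.074

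**Deaths counted with the planned censoring:** N × (λ/Λ) × mean[1 − exp(−Λf)], f uniform over the follow-up range.
- 1 to 4 years: the mean is 1 − (0.78 − 0.78⁴)/(3 × 0.2485) = 0.450, so 1056 × 0.702 × 0.450 ≈ 333.6
- 0.5 to 4.5 years: ≈ 326.3

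**Deaths to closeout, with mortality unchanged after exit:** N × mean[1 − exp(−λf)].
- 1 to 4 years: the mean is 1 − (0.84 − 0.84⁴)/(3 × 0.1744) = 0.346, so 1056 × 0.346 ≈ 365.3
- 0.5 to 4.5 years: ≈ 359.2

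**Discarded:** 365.3 − 333.6 = 31.7 (8.7%) and 359.2 − 326.3 = 32.9 (9.2%).

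**Varying mortality after exit.** With post-exit hazard rλ, the expected discarded deaths per patient followed for f years are c × {[1 − exp(−Λf)]/Λ − [exp(−rλf) − exp(−Λf)]/(Λ − rλ)}.

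| r | Discarded, 3+1 years | Discarded, 48+6 months |
|---|---|---|
| 0.25 | 9 (2.6%) | 9 (2.8%) |
| 0.5 | 17 (4.9%) | 18 (5.3%) |
| 1.0 | 32 (8.7%) | 33 (9.2%) |
| 1.5 | 44 (11.6%) | 45 (12.2%) |

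If the exit hazard were 0.15 per year (an assumption), the 3+1-year loss would be 17 to 83 deaths (5% to 21%) over the same range of r.

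**Power** for an assumed mortality hazard ratio of 0.75, two-sided 5%, 1:1 allocation, Schoenfeld: Φ(√(D/4) × |ln 0.75| − 1.96).
- D = 334: Φ(2.63 − 1.96) = 0.75
- D = 365: Φ(2.75 − 1.96) = 0.785
- Addendum schedule: 0.74 to 0.78

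**The case against.** **Ascertainment may be incomplete for exactly these patients.** Section 4.4 treats modality change and transfer as loss to follow-up, and Section 11.2 limits database linkage. A reader might infer from Section 4.1 that vital status will be known for everyone, but the documents do not support that. What stands is that Section 4.1 plans it for all enrolled patients, that Section 4.4 conflicts with that plan, and that a patient with truly unknown status can be censored when last known alive.

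**The loss is small.** A few points of power on a secondary outcome with admittedly limited power would not change the trial. This stands and limits the severity. Deaths are also reported as serious adverse events, so the safety committee does not depend on this model alone, although that route works mainly while patients are actively followed.

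**Censoring site failure at transplant or a switch to peritoneal dialysis is defensible**, because the graft is then no longer needed for hemodialysis. This also stands. It does not cover home dialysis or transfer, where the graft may still be in use and its closeout status is to be recorded. A reader might also infer that a graft lost just before a move to peritoneal dialysis escapes the definition in Section 8.1, with its "abandonment of the prior access as defined by the need for a central venous dialysis catheter" for at least a month. Section 4.5 defines total failure differently, by the need for a new access at another site to continue dialysis, and may capture that patient, so the point is not established.

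**Conclusion.** The concern holds for time to death and for the death component of the composite: the plan arranges to learn of deaths and then excludes them, with no reason that applies to death and no sensitivity analysis. The loss is about 9% of ascertainable deaths at the protocol's own rates, and about 3% to 12% across the post-exit mortality range. This rests on constant hazards, full enrolment and follow-up, complete ascertainment, and an exit rate obtained by subtraction.

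Two stronger readings go too far. A reader might infer that the mortality analysis is not intention-to-treat. However, patients stay in their randomized arms, and the protocol's explicit intention-to-treat statement concerns the primary analysis. The accurate description is exclusion of known outcomes, with possible informative censoring. A reader might also infer bias in a particular direction. Transplant may remove healthier patients while transfer or modality change removes sicker ones, and the documents give no rates by arm, so neither sign nor size can be computed.

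Severity: should fix.

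**What to change.** 1. In Section 9.2.2.4, analyse time to death, and the death component of the composite, from randomization to a common closeout date. Use all ascertained deaths and censor only at closeout or last known vital status, including withdrawal of consent.
2. Keep the censoring now planned as a sensitivity analysis.
3. For site failure, do not censor at home dialysis or transfer when access status at closeout is known. Censoring at transplant or a switch to peritoneal dialysis can stay.
4. Reconcile Section 4.4 with Section 4.1: state that leaving active follow-up through modality change or transfer does not end ascertainment of survival and access status at closeout. Note that under Section 11.2 some patients may decline or withdraw database linkage.

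The cost is a change of wording and one additional model run per outcome. Sections 4.1, 4.5 and 6.2.7 already plan the collection. The only extra effort is tracing patients who have left participating units, which Section 4.1 already implies.

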#### 9.3 Data Quality Control

As previously noted, Clinical Center data will be checked by auditors during site visits. Additional quality control checks on each Clinical Center will include 1) time from form completion to data entry, 2) time to response to data discrepancy inquiries, and 3) rates of missing forms and procedures, for example.

The quality of the DCC's work will be checked by looking at how often the study database is down, how often an ineligible patient is randomized, and number of days from the time a Clinical Center responds to a data discrepancy inquiry to the time the DCC makes a database correction, for example.

#### 10. TREATMENT EFFECTS AND SAFETY MONITORING

An External Advisory Committee (EAC), composed of independent experts in the fields of nephrology, biostatistics, and clinical trials, will review the accumulating data with regard to safety and efficacy. The members of the EAC are not involved in the conduct of the trial and have no affiliation with the drug manufacturers. Summary reports of the EAC will be submitted to all IRBs involved in the trial.

The EAC may terminate the trial early if one of the interventions (Aggrenox or placebo) is shown to be superior at an interim analysis based on the statistical stopping guideline (Section 9.1.5). The EAC will also consider comparisons of potential adverse events between the treatment arms. Conditional power calculations and estimates of the recruitment rate will also be provided at interim analyses so that the EAC can assess whether the trial should be terminated early in the event of unexpectedly low recruitment or trends in the treatment group comparison indicating futility of continuation of the study.

Serious adverse events are those that result in any of the following outcomes: death, a lifethreatening adverse experience, inpatient hospitalization or prolongation of existing hospitalization, a persistent or significant disability/incapacity, or a congenital anomaly or birth defect. All serious adverse events will be reported to the DCC within 24 hours of study personnel learning of the event. Information not available at the time of the initial report will be submitted to the DCC as a follow-up report. The DCC will be responsible for distributing safety reports to the Clinical Centers, the EAC, and NIDDK. NIDDK will submit safety information to the FDA. Summary reports of adverse events will be submitted to all IRBs monitoring the trial. Additional reporting to IRBs will be performed according to local IRB policy. Non-serious adverse events will be reported to the DCC using the appropriate data forms.

# 11. **REGULATORY CONSIDERATIONS**

#### 11.1 Institutional Review Boards (IRBs)

The protocol will be submitted to the IRB of each Clinical Center for review and approval. Clinical Centers may not recruit patients into the trial until approval of the protocol by their IRB. Protocol amendments and changes will be submitted to the IRB and approval must be received before implementation. All patients enrolled in the trial must sign and date an IRB-approved consent form and medical records release form before any study related procedures are undertaken. Study personnel will explain the study and answer all of the patient's questions before asking the patient to sign and date the consent form.

#### 11.2 Confidentiality of Patient Data

All patient data will be maintained in a secure location. Data collected from study evaluations will be identified by study identification codes. Identifying features including names and addresses will be provided to the DCC, but kept in a secure file separate from the study database. Social Security numbers will be provided to the DCC only with additional written consent from the patient, if required by the local IRB. If such consent is obtained, the Social Security number will be kept in a secure file separate from the study database and will be used to obtain patient-specific hospitalization, medical procedures, and death data from databases other than those maintained for this trial. Patients can withdraw consent for continued access to such databases at any time. Clinically relevant information obtained as a result of participation in this trial may be placed in the patient's medical record as progress notes.

# 12. ACCESS RELATED EVENTS AND PROCEDURES

#### 12.1 List of Access Events that Might Lead to Access Evaluation

- 1. Meets flow surveillance criteria for possible stenosis (see flow surveillance algorithm)
- 2. Thrombosis (loss of palpable access flow)
- 3. High venous pressures
- 4. Inability to achieve desired blood flow rate
- 5. Excessive bleeding post needle removal
- 6. Lower than desired kT/V
- 7. Inability to cannulate access
- 8. Access pain
- 9. Infection
- 10. Aneursym
- 11. Pseudo-aneursym
- 12. Arm swelling

- 13. Ischemia of distal extremity
- 14. High output state
- 15. Access hemorrhage
- 16. Neurological changes in access arm
- 17. Other

#### 12.2 List of Access Related Procedures

- 1. Imaging no intervention
  - a. Fistulogram
  - b. Doppler ultrasound
  - c. Other (e.g., MRI)
- 2. Interventions
  - a. Angioplasty done either by interventional radiology or surgery
  - b. Stent
  - c. Thrombolysis
  - d. Thrombectomy
  - e. Surgical debridement
  - f. Surgical revision (partial or complete resection of graft material; bypass of prior graft site using new arterial or venous anastomosis)
  - g. Surgical creation of new access site
  - h. Other (rotational myotomy, etc.)

